The study cut-off for analysis of the primary endpoint, ORR, corresponds to the date on which all evaluable treated participants have had at least 2 postbaseline tumor assessments, experienced confirmed objective response, or have discontinued the study for any reason. This study cut-off can be up to approximately 16 weeks (12 weeks for 2 tumor assessments and 4 weeks for confirmation of response, if needed) after the last participant's first IMP administration.

The final study cut-off date for analysis of the secondary efficacy endpoints, which include DOR and PFS, will be 4 months after the cut-off date for the primary analysis. At that time, the primary analysis of ORR and DCR will also be updated.

After the cut-off date for the analysis of secondary efficacy endpoints, participants still receiving study treatment can continue study treatment, if clinical benefit is observed, until PD, unacceptable toxicity, initiation of a new anticancer therapy, or withdrawal of participants' consent, and will continue to undergo all assessments as per the study flow chart.

The expected duration of study intervention for participants may vary, based on disease progression date; median expected duration of study per participant is estimated as 34 weeks (up to 4 weeks for screening, a median of 18 weeks for treatment, and a median of 12 weeks for end-of-treatment assessments and the safety follow-up visit).

Study interventions

Study interventions include tusamitamab ravtansine and ramucirumab. To prevent hypersensitivity reactions, each administration will be preceded by premedication.

Administration of tusamitamab ravtansine will be initiated after the completion of ramucirumab infusion. As infusion-related reactions (IRRs) may occur during or following ramucirumab administration, a 1 hour observation period following the ramucirumab infusion is mandatory prior to the initiation of tusamitamab ravtansine administration for the first 2 infusions. If the patient shows no evidence of an IRR with the first 2 infusions of ramucirumab, no observation period is required for subsequent infusions. In the event an IRR occurs thereafter, the 1 hour observation should be reinstated.

Each cycle of treatment will have a duration of 2 weeks.

Investigational medicinal products

Ramucirumab

Ramucirumab will be administered prior to administration of tusamitamab ravtansine.

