Other potential risks were observed in a limited number of patients, and clinical pictures were consistent with a presentation in patients with underlying relevant risk factors. These potential risks include Colitis ([including hemorrhagic], mainly in participants with a known history of colitis or gastrointestinal tract conditions), Cardiotoxicity (myocardial or conduction abnormalities), Hematologic cytopenias, and Hepatotoxicity, as well as Systemic acute hypersensitivity reactions (including anaphylaxis; 1). More detailed information about the known and expected benefits and risks and reasonably expected adverse events (AEs) of tusamitamab ravtansine may be found in the Investigator’s Brochure.

Potential risks for tusamitamab ravtansine and mitigation strategies to be employed in the study are summarized in [Table 2](#).

Table 2 - Risk assessment for tusamitamab ravtansine

Potential risk of clinical significance	Summary of data/rationale for risk	Mitigation strategy
Study interventions: tusamitamab ravtansine		
Microcystic keratopathy	
Nonclinical: Mitotic arrest/single cell necrosis in the cornea of the eye in mice and monkeys. In addition, brown discoloration of the cornea associated, microscopically, with minimal dark pigmentation in cornea epithelial cells in monkeys. Findings considered related to the cytotoxic properties of DM4.
 
Clinical: Main DLT in the dose escalation part of study TED13751. In study TED13751 pooled data: among the 160 patients treated at a dose level of 100 mg/m² Q2W, 51 patients (31.9%) had a corneal TEAE; of these, 13 patients (8.1%) had events ≥ Grade 3. In study TCD15054, of the 6 patients treated at a dose level of 100 mg/m² Q2W, 3 patients (50%) reported a corneal TEAE.
	
Careful collection of medical history and physical examination.
 
Assessment of ocular/visual symptoms at each visit before IMP administration.
 
Specific ocular tests at screening, whenever clinically indicated and at EOT.
 
Wearing of contact lenses is forbidden.
 
Preventive instillation of artificial tears or hyaluronic ophthalmic gel drops.
 
Curative action: dose delay and reduction; artificial tears, corticosteroid eye drops and symptomatic treatment; ophthalmologist follow-up.

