## Major changes in statistical analysis plan

# 1 INTRODUCTION

# 1.1 STUDY DESIGN

This is a Phase 2, open-label, multicenter, single-arm study to confirm the recommended dose, safety, efficacy (antitumor activity), and pharmacokinetics (PK) of tusamitamab ravtansine combined with ramucirumab in participants previously treated for gastric or gastroesophageal adenocarcinoma with CEACAM5-positive tumors.

The study will comprise 2 parts: Part 1 (Safety run-in) to assess the tolerability and to confirm the recommended dose (RD) of tusamitamab ravtansine in combination with ramucirumab; and Part 2, to assess the antitumor activity of tusamitamab ravtansine in combination with ramucirumab.

The screening phase will be performed only in prescreened participants determined to be CEACAM5-positive by immunohistochemistry (IHC) assessment.

Approximately 32 to 38 participants will be treated from approximately 21 sites to achieve a total of 32 participants treated at the RD and evaluable for activity.

The cycle duration is 14 days. The median expected duration of study per participant is estimated at 34 weeks (up to 4 weeks for screening, a median of 18 weeks for study intervention administration, a median of 12 weeks for end-of-treatment (EOT) assessments, and the safety follow-up visit).

Treatment allocation will be performed using interactive response technology (IRT). After being screened, eligible participants will receive tusamitamab ravtansine combined with ramucirumab until documented disease progression, unacceptable toxicity, new anticancer therapy initiation, death, or the participant's or Investigator's decision to stop the treatment.

This will be a 2-part study.

• Part 1 (safety run-in): participants will receive ramucirumab 8 mg/kg followed by tusamitamab ravtansine at 170 mg/m^2 at Day 1 Cycle 1, and ramucirumab 8 mg/kg followed by tusamitamab ravtansine 100 mg/m^2 at Cycle 2 Q2W in all subsequent cycles. In the case that it is decided to reduce the initial loading dose of tusamitamab ravtansine to Dose Level (DL)-1 (Table 1), a tusamitamab ravtansine loading dose of 150 mg/m^2 will be administered to participants at Day 1 of Cycle 1.

Dose Level (DL)	Tusamitamab revtansine	Ramucirumab
Starting dose	170 mg/m  Q2W Cycle 1;	8 mg/kg Q2W
-	100 mg/m  Q2W Cycle 2 and thereafter	
Minus -1 (DL-1)	150 mg/m  Q2W Cycle 1;	8 mg/kg Q2W
	100 mg/m  Q2W Cycle 2 and thereafter	

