# **Observation** period

The observation period will be divided into 4 segments:

- The **pre-treatment period** is defined as the period up to first IMP administration.
- The **on-treatment period** (ie, treatment-emergent (TE) period) is defined as the period from the first IMP administration to the last IMP administration +30 days.
- The **post-treatment period** is defined as the period from the end of the on-treatment period.

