#### Table 9 - Selections for AESIs and other AEs of interest

An overview of corneal TEAEs will be provided with the following AE categories: any corneal TEAEs, Grade  $\geq$ 3 corneal TEAEs, treatment-emergent corneal SAEs, corneal TEAEs related to IMP, Grade  $\geq$ 3 corneal TEAEs related to IMP, corneal TEAEs leading to permanent full intervention discontinuation, corneal TEAEs leading to permanent partial discontinuation of tusamitamab ravtansine, and corneal TEAEs leading to dose modification (cycle delay, dose reduction, or dose omission) of tusamitamab ravtansine.

A summary of treatment-emergent corneal events will be provided.

- Cycle of first occurrence regardless of the grade
- Cycle of first occurrence of the worst grade
- Number (%) of participants by worst grade
- Relationship to study intervention: in case of multiple occurrences in a single participant with different relationships, if any event is related, then the relationship will be considered as related for that participant
- Action taken with the study intervention: in case of multiple occurrences with different actions in a single participant, the most severe action taken will be tabulated and selected according to the following order of severity: drug withdrawn, dose reduced, drug interrupted, dose not changed
- Outcome: in case of multiple occurrences with different outcomes in a single participant, the most severe outcome will be tabulated and selected according to the following order of severity: fatal, not recovered or resolved, recovering and resolving, recovered and resolved with sequelae, recovered and resolved, unknown.

In addition, analyses on occurrence and recurrence of corneal events will be provided. An occurrence of a corneal event will be defined as 1 or a group of concomitant corneal events. A recurrence will be defined as any occurrence of corneal event starting after a previously resolved occurrence.

- The number of occurrences by participant
- The time to first onset of corneal event will be described using Kaplan-Meier curves. Time to first onset is defined as the time from the date of first IMP administration to the date of the first occurrence of the event. In the absence of an event before the analysis cut-off date, it will be censored at the end date of the treatment-emergent period, analysis cut-off date, or date of death, whichever occurs first.

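### The Kaplan-Meier curve for first corneal event censors death and end of the treatment-emergent period, so read as incidence it is biased upward; add a cumulative incidence curve or label it

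*SAP*

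**What the plan says.** SAP 3.6.2, in the part on occurrence and recurrence of corneal events, states: "The time to first onset of corneal event will be described using Kaplan-Meier curves". The clock starts at first IMP administration. Without an event before the analysis cut-off, "it will be censored at the end date of the treatment-emergent period, analysis cut-off date, or date of death, whichever occurs first". Under the Observation period heading of SAP 3.1, the treatment-emergent period "is defined as the period from the first IMP administration to the last IMP administration +30 days". SAP 1.1 lets treatment run "until documented disease progression, unacceptable toxicity, new anticancer therapy initiation, death, or the participant's or Investigator's decision to stop the treatment", and expects "a median of 18 weeks for study intervention administration".

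The SAP names no target quantity for this curve and has no competing-event rule for it. It does plan other corneal summaries:

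- **Crude counts.** SAP 3.6.2 gives the number and percentage of participants with any treatment-emergent corneal event in the TEAE overview. It also gives any, Grade 3 or higher, serious and IMP-related corneal TEAEs, and a breakdown by worst grade.
- **Timing.** The same section tabulates the cycle of first occurrence, both for any grade and for the worst grade.

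**The concern.** Kaplan-Meier treats a censored participant as someone who stays at risk and would go on to have events at the same rate as those still observed. That is right for a participant still in the treatment-emergent period when the data are cut. It is not right for one who has died. Nor is it right for one more than 30 days past the last dose, if the question is how many treated participants get a treatment-emergent corneal event: a later event is not counted, so that participant can no longer contribute one. For that question both exits are competing events.

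With a median of 18 weeks on treatment, and progression, toxicity, new therapy and death among the reasons for stopping, leaving the risk set this way is the usual course. Protocol 2.3.1 names corneal toxicity as the main identified risk of tusamitamab ravtansine. A reader who takes the height of the curve at a given week as the risk by that week would take too high a figure. The same report could show a crude percentage below the curve with nothing to explain the difference.

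**Working it through.** **Inputs from the documents**

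- Corneal rate: Protocol 2.3.1, Table 2, reports "51 patients (31.9%) had a corneal TEAE" among 160 patients given 100 mg/m² Q2W as monotherapy. Check: 51/160 = 31.9%, which reproduces.
- Treatment duration: median 18 weeks (SAP 1.1).
- End of the treatment-emergent period: last IMP + 30 days, that is 30/7 = 4.29 weeks. Apart from death or data cut-off, nobody leaves the risk set before week 4.29.
- Number treated: "Approximately 32 to 38 participants will be treated from approximately 21 sites" (SAP 1.1).

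**Assumptions, because the documents are silent**

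- Treatment time is exponential.
- 31.9% is the eventual share of treated participants with a corneal event. It is a monotherapy figure used only to set the scale.
- Onset timing is varied.

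**Direction.** Aalen-Johansen removes competing exits from the population that can still have an event; Kaplan-Meier redistributes them to those remaining. So 1-KM is never below Aalen-Johansen. In 4,000 simulated trials per scenario (n = 32 and n = 38, read at weeks 24 and 52), it was strictly higher in 98% to 100% of trials and lower in none.

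**Constant onset hazard, closed form.** Let μ = ln 2/18 = 0.0385 per week be the hazard of stopping treatment, d = 4.29, and λ the corneal hazard.

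- 1-KM targets 1 − exp(−λt).
- Cumulative incidence is CIF(t) = 1 − exp(−λd) + exp(−λd) × λ/(λ+μ) × [1 − exp(−(λ+μ)(t−d))].
- λ is set so that CIF tends to 31.9%. This gives λ = 0.0146: exp(−λd) = 0.939, λ/(λ+μ) = 0.275, and 0.061 + 0.939 × 0.275 = 0.319.

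| Week | 1-KM | CIF | Gap |
|---|---|---|---|
| 24 | 29.6% | 22.8% | 6.7 |
| 26 | 31.6% | 23.7% | 7.9 |
| 52 | 53.2% | 29.8% | 23.4 |

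Gaps are in points, from unrounded values. The simulation agrees: with n = 32, 29.6% v 22.9% at week 24 and 53.1% v 30.0% at week 52. With n = 38 the gaps are the same within 0.2 points.

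**Early onset, uniform over weeks 3 to 9 in a susceptible fraction q.** The chance of still being in the treatment-emergent period at onset is [(4.29 − 3) + (1 − exp(−μ × 4.71))/μ]/6 = 0.933. So q = 0.319/0.933 = 34.2%. From week 9 on, 1-KM targets 34.2% against a CIF of 31.9%: a gap of 2.3 points, or 0.023 × 32 = 0.7 of a participant in 32.

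**In between: onset with median 6 weeks in a susceptible fraction.** The week-26 gap is about 4.5 points.

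**Against the noise.** The standard error of 1-KM at week 26 is 8.0 to 8.7 points for onset in weeks 3 to 9, so that gap is about a quarter of it (2.3/8.7 = 0.26). It is 8.9 to 9.6 points for median-6-week onset, so that gap is about half of it (4.5/9.6 = 0.47).

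**Sensitivity.**

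- If only death is counted as competing (assumed 10% to 30% of event-free exits), the constant-hazard gap at week 52 is 3.6 to 9.4 points.
- If the whole treatment-emergent period is taken as exponential from day 1, with median 12 to 26 weeks, the week-24 gap runs from 20.0 down to 6.5 points. That version ignores the 30-day floor, so it only shows how far the answer depends on the duration distribution.

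**The case against.** The strongest reply is that incidence is already reported correctly. The crude percentages in SAP 3.6.2, on the all-treated population, say how many participants had a corneal event. With complete follow-up, or a common cut-off time, Aalen-Johansen returns the same number. This stands. A reader might infer that the report will misstate the overall frequency of corneal toxicity, or that the curve is the only account of its timing. The documents support neither: the counts by worst grade and the cycle of first occurrence are both planned. What the crude table does not give is a risk by a stated time among all treated participants, which a reader would naturally look for in the curve.

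A second reply is that the SAP uses the curve only to describe onset. It attaches no landmark probability, confidence interval, test or decision to it, and SAP 3.6 calls the safety analysis essentially descriptive. This also stands, and it sets the priority.

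A third is that Kaplan-Meier with censoring at end of exposure is a defensible description of onset while exposed, if leaving is independent of corneal risk. That is partly right. Death is a competing event in any case; end of the treatment-emergent period is one only when the target is incidence among all treated. But the SAP does not state a while-exposed target here, although it names a hypothetical strategy for DOR and PFS. Nor is the risk set purely one of exposure to tusamitamab ravtansine. Both drugs are IMPs (Protocol 6.1), and Protocol 6.5 lets either continue alone, so a participant can stay in the treatment-emergent period after tusamitamab ravtansine has stopped.

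A fourth is that onset is probably early: Protocol 4.3 says all DLT keratopathies in the main escalation phase occurred at the end of Cycle 2. If all onset is like that, the gap is about 2 points. This is the best evidence in the documents, but those are events observed within a DLT evaluation period and do not show when other corneal events begin.

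**Conclusion.** The point holds as a matter of interpretation and labelling. Read as incidence among treated participants, the planned curve is biased upward, and the direction is certain. The crude percentages remain the correct overall incidence.

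The size is not fixed by the documents. Under exponential treatment time with median 18 weeks plus 30 days, and 31.9% overall incidence, the week-26 gap is about 2 points for onset in weeks 3 to 9, about 4.5 points for onset with median 6 weeks, and about 8 points under a constant hazard. Only the constant hazard takes it to about 23 points, and only by week 52. A reader might infer that the gap is always large against the curve's own uncertainty. It is not: with onset in weeks 3 to 9 it is about a quarter of a standard error. Censoring at the analysis cut-off is administrative and raises no issue.

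Priority is low, because no dose, stopping or efficacy decision uses the curve.

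**What to change.** In SAP 3.6.2, add an Aalen-Johansen cumulative incidence curve for first treatment-emergent corneal event. Treat death, and the end of the treatment-emergent period without a corneal event, as competing events. Censor only participants still in that period at the analysis cut-off.

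If the Kaplan-Meier curve is kept, state in the SAP and in the figure title that it shows a hypothetical while-on-treatment risk and is not an estimate of incidence, and show it beside the crude number and percentage.

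The cost is a few lines of SAP text and one figure from data already collected. The downside is one more descriptive curve to explain.

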- The time to recovery will be summarized using descriptive statistics in participants who have had at least 1 recovered or resolved occurrence of a corneal event (with or without sequelae), considering the longest duration among all occurrence by participant.
- The time to recurrence will be summarized using descriptive statistics in participants who have had at least one recurrence, considering the shortest time among all recurrences by participant.

Beside the AE categorized as ocular/visual adverse events, all ocular symptoms (coded term) recorded in e-CRF will be reported as descriptive analysis. Same descriptive analysis will be done separately for ocular/visual symptoms associated to treatment-emergent corneal events (CMQ).

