#### Visual acuity test

Analyses are done on the best corrected visual acuity (BCVA) assessed using Snellen Chart method.

Frequency tables on BCVA measured during the on-treatment period will be performed separately on all participants and on participants who experienced at least one treatment-emergent corneal event:

- On the worst change from baseline: No worsening versus baseline (no line decrease), Worsening versus baseline (1 to 3 lines decrease versus baseline, or >3 lines decrease versus baseline).
- On the worst absolute value: No change versus baseline, Worsening versus baseline (BCVA equals to 20/40 or better, BCVA worse than 20/40 up to 20/200, BCVA 20/200 or worse).
- On the CTCAE worst vision decrease: BCVA equals to 20/40 or better or 1 to 3 lines decrease versus baseline, BCVA worse than 20/40 up to 20/200 or >3 lines decrease versus baseline, BCVA 20/200 or worse.

• For participants who had worsening versus baseline (at least one line decrease) on BCVA, the worst outcome on the last BCVA will be displayed: Recovered to baseline, Not recovered to baseline, Lost to follow-up or dead with ongoing corneal events.

A participant will be considered as lost to follow-up if the participant discontinued the study and did not perform any follow-up visit.

A shift table of the category of the last BCVA value (Normal (20/20 or better), worse than 20/20 up to 20/40, worse than 20/40 up to 20/200 or 20/200 or worse) versus the category of the worst BCVA value (20/40 or better, worse than 20/40 up to 20/200, 20/200 or worse) will be performed for participants who experienced at least one treatment-emergent corneal event.

For the summary table on participants who experienced at least one treatment-emergent corneal event, the worst value and the worst change from baseline are measured during any of the treatment-emergent corneal events experienced by the participant (between start date and end date of the corneal events). For summary table on all participants, all on-treatment BCVA values are considered.

The worst classification between the laterality will be considered for the worst absolute value, the worst change from baseline and the last value separately even if not measured on the same eye. If the worst absolute value is the same for both eyes, then the eye with the worst change from baseline is considered, and if identical, then the eye with the worst last value is considered.

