Participants whose baseline visual acuity had been reported in naked eye instead of BCVA (ie, whenever the baseline value was worse than the values reported during the treatment period/treatment-emergent corneal event) will be excluded from this analysis.

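### Corneal time to recovery is summarized only in participants who recovered, and naked-eye baselines are inferred from later acuity: two inexpensive corrections to descriptive safety outputs

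*SAP*

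**What the plan says.** **Recovery and recurrence (SAP 3.6.2, corneal events).** On recovery: "The time to recovery will be summarized using descriptive statistics in participants who have had at least 1 recovered or resolved occurrence", resolution with sequelae included, "considering the longest duration among all occurrence by participant". No censoring rule is given. Recurrence is conditioned in the same way: "The time to recurrence will be summarized using descriptive statistics in participants who have had at least one recurrence". Onset of the same events is handled differently: "The time to first onset of corneal event will be described using Kaplan-Meier curves", with censoring at the end of the treatment-emergent period, the cut-off or death. Unresolved events are still counted, without a duration, in the corneal outcome summary, whose severity order begins "fatal, not recovered or resolved, recovering and resolving".

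**Visual acuity (SAP 3.6.3.2).** "Analyses are done on the best corrected visual acuity (BCVA) assessed using Snellen Chart method". A baseline is taken to be naked-eye "whenever the baseline value was worse than the values reported during the treatment period/treatment-emergent corneal event", and that participant leaves the analysis. For participants whose acuity worsened, the last-outcome table has the categories "Not recovered to baseline, Lost to follow-up or dead with ongoing corneal events".

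**Context.** Protocol 2.3.1 names corneal toxicity as the main identified risk and calls it reversible. SAP 3.6 makes all safety analyses descriptive, with no testing.

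**The concern.** **(a) Time to recovery.** Entry to the summary depends on having recovered. At any cut-off, long events are the likelier ones to be unresolved, so those removed are disproportionately slow recoverers and the summary runs short. The longest-duration rule is also incomplete: it does not say what happens when one occurrence has resolved and another is ongoing, so two programmers could report different figures. This summary is the SAP's main measure of how long corneal events last.

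**(b) Visual acuity.** The exclusion is decided by comparing baseline with post-baseline values, which are the outcome.
- A genuine best corrected baseline can be removed because later readings happened to be better.
- A true naked-eye baseline followed by equal or worse acuity stays in, and can hide a real loss.
- The rule does not say whether baseline must be worse than all later values or only some.

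At stake is the description of reversibility and visual impact for the main identified risk, and nothing beyond that.

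**Working it through.** The SAP states no figure for time to recovery, so there is none to reproduce. The calculation below is an illustration.

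**Inputs from the documents**
- First enrolment 21-Nov-2021 and SAP approval 17-Jul-2023, before the primary analysis (SAP Version History): 603 days / 7 = 86 weeks.
- First cut-off about 16 weeks after the last participant's first dose (SAP 3.8).
- Keratopathy DLTs in the first-in-human study came at the end of Cycle 2 (Protocol 4.3): 2 × 2 weeks = week 4.
- Corneal event rate 51/160 = 31.9% on 100 mg/m² Q2W monotherapy (Protocol Table 2).
- 32 to 38 treated participants (SAP 1.1).

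**Assumptions (not in the documents)**
- Exponential recovery with a true median of 6 weeks, and one event per participant.
- Uniform accrual and onset at week 4. Follow-up after onset then runs from 16 − 4 = 12 weeks to 86 − 4 = 82 weeks.
- For the survival variant, median survival of 42 weeks from onset. This is borrowed from the 9.6 months for ramucirumab plus paclitaxel in Protocol 2.1.

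**Formulas.** The recovery rate is λ = ln 2 / 6 = 0.1155 per week. With follow-up uniform on (a, b), the unresolved share is U = (2^(−a/6) − 2^(−b/6)) / (λ(b − a)). If the answer is below a, the recovered-only median t solves 1 − 2^(−t/6) = (1 − U)/2.

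**Follow-up of 12 to 82 weeks**
- U = (0.2500 − 0.0001) / (0.1155 × 70) = 3.1%.
- 1 − 2^(−t/6) = 0.4845, so t = 5.7 weeks against 6.0.

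**The same, with death as a further end of follow-up**
- The combined half-life is 1/(1/6 + 1/42) = 5.25 weeks, and the share of first exits that are recoveries is 42/48 = 0.875.
- U = 0.125 + 0.875 × [2^(−12/5.25) − 2^(−82/5.25)] / (0.1320 × 70) = 0.125 + 0.019 = 14.4%.
- 0.875 × (1 − 2^(−t/5.25)) = 0.428, so t = 5.1 weeks.

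**Follow-up of 4 to 16 weeks for everyone**
- U = (0.630 − 0.157) / (0.1155 × 12) = 34.1%.
- 1 − 2^(−t/6) = 0.3296, so t = 3.5 weeks.

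Intermediate cases, by simulation: 5.4 weeks (7% unresolved) with 12 to 40 weeks of follow-up, and 5.8 weeks (3%) with 20 to 52.

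**Precision of the alternative.** If the prior rate applied here, 0.319 × 32 = 10.2 and 0.319 × 38 = 12.1 participants would have an event. In simulation with 12 events and 4 to 16 weeks of follow-up, the Kaplan-Meier median had a 10th to 90th percentile range of 2.9 to 9.2 weeks among those reached; 4% were not reached.

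**Acuity rule.** No size can be derived, because the documents give neither the frequency of naked-eye baselines nor test-retest variation. Only a direction follows. If baseline must be worse than all later values, those removed are mostly participants who did not worsen. The proportion worsened then moves from w/n to w/(n − k), which is larger. If one better value is enough, worsened participants can be removed too, and the direction is no longer fixed. The last-versus-worst shift table uses no baseline, so the exclusion serves no purpose there.

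**The case against.** **Follow-up is long enough to limit the bias.** Much of this stands. Protocol 8.2.7.2 continues ocular examinations until total resolution, the schedule of activities follows related AEs and AESIs to resolution or stabilization, and SAP 3.8 updates safety at study end. A reader might infer that the reported recovery time will be little more than half the true one. That needs the whole cohort to have only 4 to 16 weeks after onset. The 16 weeks in SAP 3.8 run from the last participant's first dose, and at least 86 weeks separate first enrolment from the primary analysis. The bias is not removed altogether, because a stabilized event is still ongoing and deaths also leave events unresolved.

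**Nothing is hidden.** A reader might infer that unresolved events vanish from the report. They do not: the corneal outcome summary and the acuity last-outcome table both count them. What is missing is their duration.

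**The SAP states its restriction and names no other target.** This also stands. The text describes a summary among participants with a resolved occurrence, so it would be wrong to say that the SAP misses a target of its own. The narrower point is that such a summary will be read as how long recovery takes.

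**The alternative measures something else.** This stands too. Time to resolution of the first occurrence is not longest duration. If 30% or 50% had a second occurrence, starting 4 weeks after the first resolved, the SAP statistic with 12 to 40 weeks of follow-up would be 6.2 or 6.8 weeks. That is longer than the first-occurrence median of 6.0. The added output could therefore be shorter or longer than the present one, and it will be imprecise.

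**The acuity exclusion errs on the cautious side.** A reader might instead infer that it flatters the treatment. On the all-values reading it tends to raise the worsening percentage. The opposite error, a naked-eye baseline left in, can hide loss. The documents do not show which dominates.

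**Conclusion.** The point holds as an inexpensive improvement to descriptive safety outputs. Time to recovery as specified conditions on recovery, is biased short, and leaves ongoing occurrences undefined. Under an assumed true median of 6 weeks, one event each, and the follow-up that the trial's dates suggest, the shortfall is about 0.3 weeks (6.0 − 5.7), or about 0.9 weeks (6.0 − 5.1) with the assumed survival. Uneven accrual, later onset or slower recovery would change these figures. The acuity rule selects on the outcome and can err in either direction; no magnitude is claimed. Neither issue touches the DLT assessment, ORR or any decision rule, and the documents give no ground for reading either as concealment of corneal risk.

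**What to change.** **(a) SAP 3.6.2**
- Add Kaplan-Meier time to resolution of the first occurrence, in all participants with a treatment-emergent corneal event.
- Censor unresolved events at the last ocular assessment, cut-off or death, and report the number unresolved.
- Keep the longest-duration summary, stated as covering resolved occurrences only.

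**(b) SAP 3.6.3.2**
- Present the baseline-referenced acuity tables with and without the exclusion, and report the number excluded.
- Do not apply the exclusion to the last-versus-worst shift table.
- Where correction status at baseline is already recorded, use it in place of the inferred rule. Protocol 8.2.2 asks only for visual acuity, so it may not be recorded; new source queries are not required.

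**Cost.** SAP wording, one additional Kaplan-Meier output and one repeat of the acuity tables. Trial conduct and sample size do not change. The price is a second recovery figure that measures a different quantity from the first and, with about 10 to 12 participants with an event, carries wide uncertainty. The text should say so beside the output.
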